8.8.2 Outcome variables

Protocol-mandated procedures, tests, and encounters are excluded.

The outcome assessments for the primary endpoint and the main secondary endpoint are described in Sections [8.1.1](#) and [8.1.2](#), respectively. The outcome assessments for the remaining secondary endpoints and all exploratory endpoints are listed below.

Secondary outcome variables

- Hospital admissions with HK as a contributing factor (based on clinical judgement and confirmed by adjudication committee, see [Appendix A 5](#)) and all-cause, respectively, including time of event, number of events, and LOS.
Hospital admissions where HK was not a contributing factor will also be collected.
- Emergency department visits with HK as a contributing factor (based on clinical judgement and confirmed by adjudication committee, see [Appendix A 5](#)) and all-cause, respectively, including time of event and number of events.
Emergency department visits where HK was not a contributing factor will also be collected.
- Outpatient visits (all-cause)
- Mean K⁺ levels
- Use of rescue therapy (see Section [6.7.1](#))
- All-cause death.

Exploratory outcomes variables

- Intensive care unit (ICU) visits
- eGFR
- Use of K-binders to treat HK post-discharge
- Dialysis initiation

- Use of RAASI.

9 STATISTICAL CONSIDERATIONS

9.1 Statistical Hypotheses

The statistical hypothesis for the primary endpoint is:

Null: No difference in the occurrence (yes/no) of a participant being NK at 180 days post-discharge between the SZC and SoC arms.

Alternate: Difference in the occurrence (yes/no) of a participant being NK at 180 days post-discharge between the SZC and SoC arms.

The statistical hypotheses for the time to event secondary endpoints (#1, #2, #4, and #6) are:

Null: No difference in event rates corresponding to time to first occurrence of any component of the composite outcome between the SZC and SoC arms.

Alternate: Difference in event rates corresponding to time to first occurrence of any component of the composite outcome between the SZC and SoC arms.

The statistical hypothesis for secondary endpoint #3 is:

- Null: No difference in the incidence rates of hospital admission or ED visit with HK as a contributing factor between the SZC and SoC arms.

Alternate: A difference in the incidence rate of hospital admission or ED visit with HK as a contributing factor between the SZC and SoC arms.

9.2 Sample Size Determination

The sample size calculation for this study is based on the main secondary endpoint (Time to first occurrence of any component of all-cause hospital admission, or ED visit with HK as a contributing factor, or all-cause death or use of rescue therapy for HK at any time post-discharge up to 180 days); the sample size would be smaller if based on the primary endpoint of maintained NK.

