9.2.1 Primary Endpoint

For the primary endpoint a sample size estimate would calculate;

- Two group χ^2 test
- Significance level: 5% (two-sided)
- Power: 80%

- Proportions with NK (K^+ between 3.5 and 5.0 mmol/L, inclusive) at 180 days post-discharge), ([Davis et al, 2019](#); [Spinowitz et al, 2019](#)):
 - Arm A (SZC): 0.88
 - Arm B (SoC): 0.59

The above test specifics and assumptions yield a sample size of 36 participants per arm (total N = 72). Assuming a 20% drop out rate from enrolment to randomisation and a 20% drop out post-discharge (post-randomisation), a total of approximately 113 participants will be enrolled. This is exceeded by the number of participants required for the secondary endpoint sample size calculation (Section [9.2.2](#))

The above effect-size assumptions do not contemplate the potential impact of RAASi down-titration on response. Since this is expected to diminish the response rate in the SoC arm relative to the treatment arm, these conservative assumptions should provide a slight underestimate of power.

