9.3 Populations for Analyses

The following populations are defined:

Table 7 **Populations for Analysis**

Analysis Set	Description	Treatment Assignment
Full Analysis Set (FAS)	The FAS, the primary, secondary, and exploratory efficacy analysis set, will include all randomised participants	Participants will be analysed according to their randomised treatment.
Per Protocol Set (PPS)	The FAS participants without any important protocol deviations leading to exclusion from the PPS.	Participants will be analysed according to their randomised treatment.
Safety Set Open (SSO)	The SSO will include all participants who receive at least one dose of sodium zirconium cyclosilicate (SZC) during the study up until discharge/randomisation.	Participants will be analysed as a single group.
Safety Set Randomised (SSR)	The SSR will include all randomised participants receiving at least 1 dose of SZC post-discharge in Arm A, and all randomised participants in Arm B.	Participants will be analysed according to treatment actually received.

The number of participants in each analysis set, and the number excluded and associated reasons, will be summarised by treatment group and overall. In addition, the following periods will be defined for the purpose of reporting:

Table 8 **Analysis Periods**

Period	Description
Inpatient period	The inpatient period refers to the period from the date of first study intervention dispensation of sodium zirconium cyclosilicate until the date of randomisation at discharge (exclusive).
Outpatient period	The outpatient period refers to the period from the date of randomisation until the earliest date of last assessment during the follow-up period, withdrawal of consent, last contact with the participant, or death (inclusive).

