9.4.3 Efficacy

9.4.3.1 Primary Endpoints

Occurrence (yes/no) of NK (K^+ between 3.5 and 5.0 mmol/L, inclusive) at 180 days post-discharge

- Population: FAS
- Endpoint: Occurrence (yes/no) of NK (K^+ between 3.5 and 5.0 mmol/L, inclusive) at 180 days post-discharge
- Intercurrent event strategy: Participants who discontinue treatment with a K^+ measurement at 180 days post-discharge will have this value used irrespective of treatment discontinuation (treatment policy strategy). Use of rescue therapy for HK will be considered to be non-response (composite variable strategy). The RAASI down-titration (including discontinuation) will be considered to be non-response (composite variable strategy). Participants who die of any cause prior to 180 days post-discharge or who are lost to follow-up for any reason will be considered to be non-response (composite variable strategy).
- Population level summary (analysis): Logistic regression analysis with response (occurrence) as the dependent variable and randomised treatment group as the

independent variable. The odds ratio along with the two-sided 95% confidence intervals and two-sided p-value (significance declared < 0.05) will be displayed.

Sensitivity Analyses

The analyses of the primary endpoint will be repeated by varying the estimand:

- Population level summary (analysis): Providing there are sufficient participants within each covariate to support the analysis, the logistic regression model will include randomised treatment group and the following baseline variables: age (as a spline), sex, presence of heart failure, diabetes, RAASi use, CKD stage, and baseline K⁺ (mild HK defined by K⁺ between > 5.0 and ≤ 5.5 mmol/L and moderate/severe HK defined by K⁺ between > 5.5 and ≤ 6.5 mmol/L) as independent variables.
- Intercurrent event strategy: As primary estimand, but participants needing rescue therapy for HK will follow the treatment policy strategy (ie, regardless of the intercurrent event).
- Intercurrent event strategy: As primary estimand, but participants with RAASi down-titration (including discontinuation) will follow the treatment policy strategy (ie, regardless of the intercurrent event).
- Intercurrent event strategy: As primary estimand but participants who die or are lost to follow-up prior to 180 days post-discharge will not be evaluated (completers analysis only).

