### **3.3.1.4 Handling of Missing Data**

#### **3.3.1.4.1 Handling of Missing Efficacy Data**

Participants with missing data for the primary efficacy endpoint of occurrence (yes/no) of normokalaemia (NK) ( $K^+$  between 3.5 and 5.0 mmol/L, inclusive) at 180 days post-discharge will be treated as non-responders for the main analysis. Additionally, participants who receive rescue medication for HK during the outpatient period will also be deemed as non-responders, regardless of any subsequent measurement for  $K^+$ .

$K^+$  measurements up to 180 days post-discharge will be analysed using mixed-effects models repeated measures, which assumes that missing outcomes are missing at random (MAR). Details of this analysis are provided in section 4.2.13.

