### 4.2.2.3 Handling of Dropouts and Missing Data

Participants who die prior to 180 days post-discharge, who are missing an assessment at visit 10 or who are lost to follow-up for any reason will be considered to be non-response for the primary analysis.

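### The primary-endpoint sample size treats dropouts as leaving the analysis, but the analysis counts them as non-responders; at the plan's 20% dropout, 65 per arm gives 77% power and the primary does not need a smaller sample

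*Protocol*

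**What the plan says.** Protocol 9.2 bases the sample size on the main secondary endpoint and adds that "the sample size would be smaller if based on the primary endpoint of maintained NK". Section 9.2.1 supports this with a two-group chi-square test (two-sided 5%, 80% power) of 0.88 against 0.59. It reports 36 per arm and, after 20% dropout before randomisation and 20% after, 113 enrolled. It then states: "This is exceeded by the number of participants required for the secondary endpoint sample size calculation". Section 9.2.2 gives that larger number as 52 evaluable per arm and 163 enrolled; Section 4.1 gives about 130 randomised.

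Section 9.2.1 closes by saying that RAASi down-titration has been left out of the rates and that "these conservative assumptions should provide a slight underestimate of power".

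On the analysis, Protocol 9.3 says: "The FAS, the primary, secondary, and exploratory efficacy analysis set, will include all randomised participants". Protocol 9.4.3.1 says that participants "lost to follow-up for any reason will be considered to be non-response". The SAP agrees. Under 3.3.1.4.1, participants with missing primary data "will be treated as non-responders for the main analysis", and 4.2.2.3 applies the rule to those "who are missing an assessment at visit 10 or who are lost to follow-up for any reason will be considered to be non-response".

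**The concern.** Dividing by 0.8 after randomisation is the right correction when dropouts are removed and the remaining participants are compared at the assumed rates. Here dropouts stay in the denominator as failures. The number analysed does not shrink; the response rates do, and so does the difference between arms. Section 9.2.1 mentions only an influence that would raise power (RAASi down-titration) and not this one, which lowers it.

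A reader of 9.2 and 9.2.1 would infer that the primary endpoint has power to spare: at 52 evaluable per arm the stated rates give 93%. The primary is also first in the fixed testing order (SAP 3.3.4), so the main secondary endpoint, which set the sample size, is formally tested only if the primary succeeds.

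**Working it through.** **Inputs.** Rates 0.88 and 0.59, two-sided 5%, 80% power, and 20% dropout before and 20% after randomisation (Protocol 9.2.1); 1:1 allocation and 130 randomised, so 65 per arm (4.1); all randomised participants analysed (9.3); dropouts and missing values as non-response (9.4.3.1; SAP 3.3.1.4.1 and 4.2.2.3).

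**Formula** (chi-square, pooled variance under the null, *p̄* the mean of the two rates, *q* = 1 − *p*):

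n per arm = [1.960 √(2p̄q̄) + 0.842 √(p₁q₁ + p₂q₂)]² / (p₁ − p₂)²

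power = Φ{ [(p₁ − p₂)√n − 1.960 √(2p̄q̄)] / √(p₁q₁ + p₂q₂) }

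**Step 1: reproduce the plan.** With 0.88 and 0.59, p̄ = 0.735 and n = (1.960 × 0.624 + 0.842 × 0.589)² / 0.29² = 35.2, so 36 per arm. Enrolment is 72 / (0.8 × 0.8) = 112.5, so 113. Both figures match 9.2.1. For the main secondary, 104 / 0.64 = 162.5, so 163, and 104 / 0.8 = 130 randomised; these also match.

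**Step 2: apply the analysis rule.** With 20% counted as non-response in each arm, 0.88 × 0.8 = 0.704 and 0.59 × 0.8 = 0.472, so p̄ = 0.588 and the difference is 0.232.

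- n = (1.960 × 0.696 + 0.842 × 0.676)² / 0.232² = 69.5, so 70 randomised per arm: 140 randomised and 140 / 0.8 = 175 enrolled, against 130 and 163 planned.
- Power at 65 per arm = Φ[(0.232 × √65 − 1.364) / 0.676] = Φ(0.748) = 77.3%.
- The 9.2.1 design itself randomises 72 / 0.8 = 90, or 45 per arm. Its power is Φ[(0.232 × √45 − 1.364) / 0.676] = Φ(0.284) = 61.2%, not 80%.

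Exact calculation at 65 per arm gives 77.6% for the chi-square test and 76.8% for the Wald test from a treatment-only logistic model.

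**Step 3: vary the loss, equal in both arms.**

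| Lacking a Day 180 value | Analysed rates | n per arm for 80% | Power at 65 per arm |
|---|---|---|---|
| 10% | 0.792 v 0.531 | 51 | 89.1% |
| 15% | 0.748 v 0.502 | 60 | 83.5% |
| 17.5% | 0.726 v 0.487 | 65 | 80.5% |
| 20% | 0.704 v 0.472 | 70 | 77.3% |
| 25% | 0.660 v 0.443 | 81 | 70.8% |

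Power at 65 per arm is 80% when loss is 17.9%.

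**Step 4: unequal loss and other failures (assumed values, 65 per arm).** Loss of 18% SZC and 22% SoC gives 87%; 22% and 18% gives 65%. With 20% loss in both arms, further RAASi or rescue failure among the remaining responders of 5% SZC and 10% SoC gives 81%, 5% and 15% gives 87%, and 10% in both gives 67%.

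**Step 5: the other reading of the rates.** If 0.88 and 0.59 already count missing values as failures, the need is 36 randomised per arm, enrolment is 72 / 0.8 = 90, and power at 65 per arm is 97%. The claim in 9.2 is then true, but 113 is too large.

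**The case against.** The 77% rests on three conditions that the plan does not spell out: that the rates are among participants with a Day 180 value, that every one of the 20% lacks one, and that loss is equal between arms. The second may be pessimistic: treatment discontinuers are followed (Protocol 7.1.1), any Day 180 value they have is used, and withdrawal is expected to be uncommon (7.2). The shortfall is five participants per arm and vanishes about two points below a round planning figure; an unpooled normal approximation gives 79.0%. The plan also expects RAASi down-titration to reduce SoC response relative to SZC, and a 2% relative cut in SoC response alone restores 80.5%. Finally, 36 evaluable per arm is a coherent basis for the completers analysis, and on that basis 36 is below 52.

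Most of this limits the size of the problem rather than removing it. Inflating separately for dropout, with one 20% rate for both arms, is the plan's own choice, and it points to evaluable-only rates. The completers analysis is a sensitivity analysis, so it cannot justify the size for the primary analysis. The other reading of the rates makes 113 wrong as well. What stands is that lower loss or a differential RAASi effect could bring power back above 80%, so the net direction is not established. Section 9.2.1 nevertheless states one.

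**Conclusion.** The concern holds. The post-randomisation inflation in 9.2.1 does not match the primary analysis, and 113 enrolled is right under neither reading of the rates. With evaluable-only rates and the plan's 20% lost equally in both arms, the primary needs 70 randomised per arm rather than fewer than the 65 planned, and power at 65 is 77%: a modest shortfall of about 3 points, or 10 randomised participants. The calculation behind 36 and 113 delivers 61% rather than 80%.

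The arithmetic is firm. The size depends on the actual proportion without a Day 180 value, its balance between arms, and what the cited rates represent, which the documents do not say. The RAASi remark is sound for RAASi down-titration alone, but does not show that power overall is understated. Type I error is unaffected.

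**What to change.** Amend the text of Protocol 9.2 and 9.2.1:

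- State whether 0.88 and 0.59 are rates among participants with a Day 180 value.
- If they are, restate the calculation under the non-responder rule: 0.704 against 0.472 at 20% loss, 70 per arm for 80% power, 77% at 65 per arm, and 80.5%, 83.5% and 89% at 17.5%, 15% and 10% loss. If they already count missing values as failures, remove the post-randomisation inflation (90 enrolled).
- Delete or qualify the statements in 9.2 and 9.2.1 that the primary needs fewer participants.
- Limit the closing remark to RAASi down-titration, and add that counting dropouts as non-responders lowers power, so the net direction is not established.

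A cross-reference to the testing order is enough on gatekeeping, since Protocol 9.4.1 and SAP 3.3.4 already state it.

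The cost is a text correction and, on the evaluable-only reading, a slightly less favourable stated power. Enrolment, analysis and type I error do not change.

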9.2.1 Primary Endpoint

For the primary endpoint a sample size estimate would calculate;

- Two group χ^2 test
- Significance level: 5% (two-sided)
- Power: 80%

- Proportions with NK (K^+ between 3.5 and 5.0 mmol/L, inclusive) at 180 days post-discharge), ([Davis et al, 2019](#); [Spinowitz et al, 2019](#)):
 - Arm A (SZC): 0.88
 - Arm B (SoC): 0.59

The above test specifics and assumptions yield a sample size of 36 participants per arm (total N = 72). Assuming a 20% drop out rate from enrolment to randomisation and a 20% drop out post-discharge (post-randomisation), a total of approximately 113 participants will be enrolled. This is exceeded by the number of participants required for the secondary endpoint sample size calculation (Section [9.2.2](#))

The above effect-size assumptions do not contemplate the potential impact of RAASi down-titration on response. Since this is expected to diminish the response rate in the SoC arm relative to the treatment arm, these conservative assumptions should provide a slight underestimate of power.

9.2.2 Main Secondary Endpoint

Prior data: Based on assumptions over a 6-month period of 16.2% all-cause hospitalisation for SZC arm ([Pollack et al, 2023](#)) and 40% for SoC arm ([Thomsen et al; 2017](#), [Kanda et al; 2020](#), [Horne et al; 2019](#)), 0.8% ED visits with HK as a contributing factor in the SZC arm ([Pollack et al; 2023](#)) and 3.2% for SoC ([Tafesse et al; 2020](#), [Kashihara et al; 2019](#), [Kanda et al; 2020](#)), it is assumed that 17% and 43.2% of patients in the SZC and SoC arm will experience an event respectively.

Sample size estimate:

- Log-Rank Test for Equality of Survival Curves
- Significance level: 5%
- Power: 80%
- Hazard ratio (HR; SZC/SoC): 0.329
- Proportions without the main secondary composite outcome (event-free) at 180 days post-discharge:
 - Arm A (SZC): 83% (17% with the outcome/event of interest)
 - Arm B (SoC): 56.8% (43.2% with the outcome/event of interest).

The above test specifics and assumptions yield a sample size of 52 evaluable participants per arm (total N = 104). Assuming a 20% drop-out rate from enrolment to randomisation, and a 20% drop out post-randomisation, a total of approximately 163 participants will be enrolled.

9.3 Populations for Analyses

The following populations are defined:

Table 7 **Populations for Analysis**

Analysis Set	Description	Treatment Assignment
Full Analysis Set (FAS)	The FAS, the primary, secondary, and exploratory efficacy analysis set, will include all randomised participants	Participants will be analysed according to their randomised treatment.
Per Protocol Set (PPS)	The FAS participants without any important protocol deviations leading to exclusion from the PPS.	Participants will be analysed according to their randomised treatment.
Safety Set Open (SSO)	The SSO will include all participants who receive at least one dose of sodium zirconium cyclosilicate (SZC) during the study up until discharge/randomisation.	Participants will be analysed as a single group.
Safety Set Randomised (SSR)	The SSR will include all randomised participants receiving at least 1 dose of SZC post-discharge in Arm A, and all randomised participants in Arm B.	Participants will be analysed according to treatment actually received.

The number of participants in each analysis set, and the number excluded and associated reasons, will be summarised by treatment group and overall. In addition, the following periods will be defined for the purpose of reporting:

Table 8 **Analysis Periods**

Period	Description
Inpatient period	The inpatient period refers to the period from the date of first study intervention dispensation of sodium zirconium cyclosilicate until the date of randomisation at discharge (exclusive).
Outpatient period	The outpatient period refers to the period from the date of randomisation until the earliest date of last assessment during the follow-up period, withdrawal of consent, last contact with the participant, or death (inclusive).

9.4 Statistical Analyses

The SAP will be drafted and approved within 90 days of the date of the first participant enrolled, and any further changes during the course of the study will be finalised prior to Database Lock. The SAP will include a more technical and detailed description of the statistical analyses described in this section. This section is a summary of the planned statistical analyses of the most important endpoints including primary and key secondary endpoints.

9.4.1 General Considerations

The full analysis set (FAS) will be the primary analysis set for the efficacy analyses, while the safety set randomised (SSR) will be used for the safety analyses. Safety analyses will also be performed for the safety set open (SSO). Data from all screened participants will be used to

describe the flowchart of participants from screening to fulfilment of eligibility criteria and randomisation.

All baseline characteristics, efficacy, and safety variables will be summarised using descriptive statistics as appropriate. Continuous variables will be summarised by descriptive statistics (including number of participants [n], mean, standard deviation, minimum, median, and maximum). Categorical variables will be summarised with frequencies and percentages. The extent of missing data will be reported.

To control for type I error, a hierarchical testing procedure will be followed when formally testing the primary and secondary efficacy analysis endpoints. The hierarchical testing procedure will follow a stepwise algorithm where each endpoint is only formally tested if the preceding null hypothesis is rejected (two-sided p-value < 0.05). If the preceding null hypothesis is not rejected, then the evaluation of the endpoint will be reduced to that of an exploratory endpoint. A draft order for hierarchical testing is outlined in the current order described for the primary and secondary objectives (see Section 3), and the final order will be detailed in the SAP.

The endpoint and statistical analysis sections follow the [ICH E9 \(R1\) addendum](#) on estimands and sensitivity analyses in clinical trials, including the language for strategies to address intercurrent events:

Treatment Policy Strategy

The occurrence of the intercurrent event is considered irrelevant in defining the treatment effect of interest: the value for the variable of interest is used regardless of whether or not the intercurrent event occurs. For example, when specifying how to address the use of additional medication as an intercurrent event, the values of the variable of interest are used regardless of whether or not the participant takes additional medication.

Hypothetical Strategies

A scenario is envisaged in which the intercurrent event would not occur, or that different intercurrent events would occur or that intercurrent events would occur with alternative frequency: the value of the variable to reflect the clinical question of interest is the value which the variable would have taken in the hypothetical scenario defined. A wide variety of hypothetical scenarios can be envisaged. For example, for a participant that will suffer an AE and discontinue treatment, it might be considered whether the same participant would not have the AE or could continue treatment in spite of the AE.

Composite Variable Strategies

An intercurrent event is considered in itself to be informative about the participant's outcome and is therefore incorporated into the definition of the variable. For example, a participant who discontinues treatment because of toxicity may be considered not to have been

successfully treated. If the outcome variable was already success or failure, discontinuation of treatment for toxicity would simply be considered another mode of failure. Terminal events, such as death, are perhaps the most salient example of the need for the composite strategy.

While On Treatment Strategies

For this strategy, response to treatment prior to the occurrence of the intercurrent event is of interest. Terminology for this strategy will depend on the intercurrent event of interest (eg, “while alive”, when considering death as an intercurrent event). If a variable is measured repeatedly, its values up to the time of the intercurrent event may be considered relevant for the clinical question, rather than the value at the same fixed timepoint for all participants. Like the composite strategy, the while on treatment strategy can be thought of as impacting the definition of the variable.

